Vomiting	Grade 3 (Tube feeding, TPN, or hospitalization indicated)	Delay patritumab deruxtecan until resolved \leq Grade 1, and consider treatment with antiemetics and / or corticosteroids as per Investigator's judgement and local practice/guidelines, then: 
 • If resolved to \leq Grade 1 in ≤ 7 days, resume patritumab deruxtecan. • If resolved to \leq Grade 1 in > 7 days, then reduce patritumab deruxtecan by 1 dose level.
	Grade ≥ 4	Discontinue patient from patritumab deruxtecan.
Premedicate with a two or three drug combination regimen (e.g., dexamethasone with either a 5-HT3 receptor antagonist or an NK-1 receptor antagonist as well as other drugs as indicated) for prevention of chemotherapy-induced nausea and vomiting (CINV).		
Diarrhea/Colitis	Grade 3	Delay patritumab deruxtecan until resolved \leq Grade 1, and consider treatment per local practice/guidelines, then: 
 • If resolved to \leq Grade 1 in ≤ 7 days, resume patritumab deruxtecan. • If resolved to \leq Grade 1 in > 7 days, then reduce patritumab deruxtecan by 1 dose level.
	Grade 4 (Life-threatening consequences; urgent intervention indicated)	Discontinue patient from patritumab deruxtecan.
Mucositis oral	Grade 3	Delay patritumab deruxtecan until resolved \leq Grade 1, and consider treatment per local practice/guidelines, then: 
 • If resolved to \leq Grade 1 in ≤ 14 days, resume patritumab deruxtecan. • If resolved to \leq Grade 1 in > 14 days, then reduce patritumab deruxtecan by 1 dose level.

CONFIDENTIAL

	Worst Toxicity NCI CTCAE Version 5.0 Grade (unless otherwise specified)	Schedule Modification for Patritumab deruxtecan
	Grade 4 (Life-threatening consequences; urgent intervention indicated)	Discontinue patient from patritumab deruxtecan.
Other adverse events (Non-laboratory or Laboratory)	Grade 3	Delay patritumab deruxtecan until resolved \leq Grade 1, or baseline, then: 
 • If resolved in ≤ 7 days, resume patritumab deruxtecan. • If resolved to in > 7 days, then reduce patritumab deruxtecan by 1 dose level.
	Grade 4 (Life-threatening consequences; urgent intervention indicated)	Discontinue patient from patritumab deruxtecan.

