6. DOSE MODIFICATIONS

If toxicity occurs, the toxicity will be graded using the NCI CTCAE Version 5.0, and appropriate supportive care treatment will be administered to decrease the signs and symptoms thereof. Dose adjustments will be based on the organ system exhibiting the greatest degree of toxicity.

Doses of patritumab deruxtecan will be modified based on hematologic and non-hematologic toxicity. If dose reductions are necessary, they will be permanent for the remainder of the treatment. Any patient requiring a toxicity-related dose delay of more than 18 weeks (126 days) from the last patritumab deruxtecan dose must be discontinued from the study, unless discussed with the Medical Monitor for extenuating circumstances. During the time of any dose delay, scheduled CT/MRI scans should continue as per protocol, and subjects should fulfill all of the following criteria:

- Study drug may be resumed with confirmation of continued benefit per RECIST 1.1. Scans should be performed at the frequency defined per protocol while the drug is being held.
- At minimum, 1 restaging scan must be done within 6 weeks prior to restarting the study drug.
- Investigational product is restarted within the guidance of the treatment management guidelines for patritumab deruxtecan, if appropriate.
- No prohibited concomitant medications have been administered since the last dose of patritumab deruxtecan.

If toxicities occur that are \leq Grade 2, they should be managed symptomatically, if possible, and the patient should be re-treated without a dose reduction. If toxicities occur that are \geq Grade 3, treatment should be withheld until resolution to \leq Grade 1 or to the baseline value (if the baseline value was $>$ Grade 1). Treatment should then be re-instituted, if medically appropriate, at the next lower dose level (see Table 2).

The dose level reductions to be used in this study are presented in Table 2.

CONFIDENTIAL

Table 2 Dose Level Modifications

Dose Level	Patritumab deruxtecan
Starting Dose	5.6 mg/kg
Dose Level -1	4.8 mg/kg
Dose Level -2	3.2 mg/kg

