6.2 Dose Modifications due to Non-Hematologic Toxicity

Table 4 Dose Modifications Due to Non-Hematologic Toxicities

	Worst Toxicity NCI CTCAE Version 5.0 Grade (unless otherwise specified)	Schedule Modification for Patritumab deruxtecan
General disorders and administration site conditions		

CONFIDENTIAL

	Worst Toxicity NCI CTCAE Version 5.0 Grade (unless otherwise specified)	Schedule Modification for Patritumab deruxtecan
Infusion related reaction (e.g., same reduced rate as previous infusion)	Grade 1 (Mild transient reaction; infusion interruption not indicated; intervention not indicated)	If infusion related reaction (such as fever and chills, with and without nausea/vomiting, pain, headache, dizziness, dyspnea, hypotension) is observed during administration, the infusion rate should be reduced by 50% and patients should be closely monitored. If no other reactions appear, the subsequent infusion rate could be resumed at the initial planned rate.
	Grade 2 (Therapy or infusion interruption indicated but responds promptly to symptomatic treatment (e.g. antihistamines, nonsteroidal anti-inflammatory drugs [NSAIDs], narcotics, IV injection fluids); prophylactic medications indicated for ≤24 hours)	Patritumab deruxtecan infusion should be interrupted. Symptomatic treatment (e.g., antihistamines, NSAIDs, narcotics, IV fluids) should be started. If the event resolves or improves to Grade 1, infusion can be re-started at a 50% reduced infusion rate. Upon restart, if Grade 2 symptoms recur, no further patritumab deruxtecan should be administered at that visit. The amount of patritumab deruxtecan infused must be recorded in the eCRF. Subsequent infusions should be conducted at the 50% reduced infusion rate.
	Grade 3 (Prolonged [e.g. not rapidly responsive to symptomatic medication and/or brief interruption of infusion]; recurrence of symptoms following initial improvement; hospitalization indicated for clinical sequelae)	Administration of patritumab deruxtecan should be discontinued immediately and permanently. Urgent intervention indicated. Antihistamines, steroids, epinephrine, bronchodilators, vasopressors, IV fluid therapy, oxygen inhalation etc., should be administered as clinically indicated.
	Grade 4 (Life-threatening consequences; urgent intervention indicated)	

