8.1.2 Preparation and Administration of Patritumab deruxtecan (U3-1402)

Patritumab deruxtecan (U3-1402) is administered as an IV infusion over approximately 90 minutes on Day 1 of Cycle 1. If there are no infusion-related reactions after this initial dose, then subsequent doses of patritumab deruxtecan will be infused over approximately 30 minutes on Day 1 of each subsequent cycle (Q3W).

Preparation and administration instructions will be provided in the pharmacy manual.

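### Table 4 assigns an infusion reaction that recurs on restart to two rows, one stopping the drug for that visit and the other stopping it permanently

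*Combined protocol and SAP*

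**What the plan says.** Section 6 sets the grading system: "the toxicity will be graded using the NCI CTCAE Version 5.0". The grade column of Table 4 in Section 6.2 is headed "Worst Toxicity NCI CTCAE Version 5.0 Grade (unless otherwise specified", so a patient enters the table at the worst grade reached.

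For infusion-related reactions, the Grade 2 row interrupts the infusion, starts symptomatic treatment, and then allows a restart: "If the event resolves or improves to Grade 1, infusion can be re-started at a 50% reduced infusion rate". It goes on to recurrence: "Upon restart, if Grade 2 symptoms recur, no further patritumab deruxtecan should be administered at that visit". After an instruction to record the amount infused, it closes with "Subsequent infusions should be conducted at the 50% reduced infusion rate".

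The Grade 3 row gives its definition as a list that begins with prolonged reactions and continues with "recurrence of symptoms following initial improvement; hospitalization indicated for clinical sequelae". The action, printed against Grade 3 with none printed separately for Grade 4, is "Administration of patritumab deruxtecan should be discontinued immediately and permanently".

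**The concern.** Restarting after improvement is what the Grade 2 row itself permits, so recurrence on restart is a foreseeable next step and the row plans for it. Yet the same sequence appears in the Grade 3 definition, with no exception for a restart and no minimum severity for the returning symptoms. The two rows then give opposite answers on whether the patient receives the drug again.

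Two things are at stake. The first is patient safety. A patient handled under one row may be given further infusions that the other row rules out. A patient handled under the other loses treatment that the first row allows. With about 10 sites (Synopsis), the decision is taken locally and quickly, and each site could cite the protocol for what it did.

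The second is the safety data. Section 10.4.3 summarises adverse events by maximum CTCAE grade and, separately, those leading to treatment discontinuation. The same clinical event could be entered as Grade 2 without discontinuation or as Grade 3 with it.

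**Working it through.** The plan states no figure on this point and no arithmetic is needed. The check is to follow one patient through the two rows.

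| Step | Grade 2 row | Grade 3 row |
|---|---|---|
| 1. Grade 2 reaction | Interrupt and treat | Not yet met |
| 2. Resolves or improves to Grade 1 | Restart allowed at half rate | Not yet met |
| 3. Grade 2 symptoms return on restart | Covered expressly; no more drug at this visit | Definition met: symptoms have recurred after initial improvement |
| 4. Next cycle | Later infusions described, at half rate | None; discontinuation is permanent |

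At step 3 both rows describe the patient. At step 4 their instructions cannot both be followed.

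Possible ways out within the documents:

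- **Worst-grade rule.** Applied literally, the column header moves this patient to Grade 3 at step 3. The recurrence sentence in the Grade 2 row would then apply to nobody, so this reading does not make the two rows agree.
- **The header's exception for cases specified otherwise.** It permits departures from CTCAE grading but does not name this row or give an order of precedence. The Grade 3 row carves nothing out.
- **A narrow reading of the closing Grade 2 sentence.** Suppose "Subsequent infusions should be conducted at the 50% reduced infusion rate" covers only reactions that did not recur. The recurrence sentence still limits the stop to one visit, which conflicts with a permanent stop.
- **Other sections.** Section 3.3 (discontinuation) and Section 8.1.2 (administration) do not address recurrence on restart. Section 6 has general rules for toxicities up to Grade 2 and from Grade 3 upward, but does not say which grade this event carries.
- **Amendment history.** Neither the Amendment 5 summary nor the earlier summaries in Appendix F mention these rows. Both instructions are current text.

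One reading is assumed: that the semicolons in the Grade 3 definition separate alternatives. The same table uses them that way elsewhere, for instance in the Grade 4 entry for QT prolongation, which lists different arrhythmic findings.

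**The case against.** The best defence is that the specific governs the general. The Grade 2 row sets out this exact sequence and calls what returns Grade 2 symptoms. The header allows exceptions. The Grade 3 criterion could be meant for symptoms that return after improvement without re-exposure, since it follows the item on reactions that respond poorly to treatment. This is a reasonable reading, and it means divergence between sites is possible rather than certain. But the table does not state it, and a site applying the worst-grade header has equally good text on its side.

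The defence is also right that the event may be rare. The documents give no infusion-reaction rate. In the earlier study summarised in Section 1.1.3, such reactions are not among the listed events above 20%, the Grade 3 or higher events above 5%, or the serious events in more than one patient. Discontinuation for any treatment-emergent event was 12 of 144 (8.3%). The sequence here also requires a Grade 2 reaction, improvement, restart and recurrence.

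Two stronger readings are tempting, and the documents do not support them.

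- **That the half rate has no fixed reference.** Section 8.1.2 uses about 90 and about 30 minutes, so halving gives 2 × 90 = 180 or 2 × 30 = 60 minutes, a threefold difference. But the shorter infusion is conditional: "If there are no infusion-related reactions after this initial dose, then subsequent doses of patritumab deruxtecan will be infused over approximately 30 minutes". A patient who reacts in Cycle 1 does not meet that condition; one who first reacts later does. The threefold gap compares two different patients, not two readings for one. Section 8.1.2 also refers to a pharmacy manual that is not among the documents.
- **That each affected patient moves ORR or PFS-6 by 1/20 = 5.0 points in a Part B subgroup or 1/21 = 4.8 points in Part Z.** These are ceilings. Part B subgroups are pooled with matching Part A patients; in the example in Section 10.2, with 32 patients, the ceiling is 1/32 = 3.1 points. Nor does stopping treatment itself make a patient a PFS-6 failure: Section 10.4.2 ties failure to leaving the study or lacking a tumour evaluation after six months, and Sections 7.4.1 and 7.4.3 continue imaging after treatment stops without progression.

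**Conclusion.** The point holds as an internal contradiction in Table 4. For a reaction that improves and then recurs on restart, the Grade 2 and Grade 3 rows give incompatible instructions for later cycles, and no text sets precedence.

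Its size is limited and cannot be put as a number. Each such event could carry either of two grades and could be counted, or not, as leading to discontinuation; how many will occur is unknown. The sample size and the Table 5 intervals are untouched. The conclusion rests on the wording alone, with the Grade 3 criteria read as alternatives. It matters despite probable rarity because it concerns whether an individual patient is given the drug again.

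**What to change.** The sponsor's medical team should reconcile the Grade 2 and Grade 3 rows for infusion-related reactions so that recurrence on restart falls under one grade with one action, and the other row no longer describes the same event. Which grade and which action is a clinical decision on which this review takes no position.

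The cost is a wording change in one block of Table 4, made by amendment, with the pharmacy manual checked for consistency and sites notified. If any such events occurred before the change, their recorded grade and discontinuation status should be checked for consistency before the safety tables are produced.

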Patients in the subgroups from Part A that are expanded in Part B will be included in a combined subgroup for presentation (e.g., if 12 ER high/HER-3 high patients are treated in Part A, and that subgroup treats 20 additional patients in Part B, they would be added to the affiliated Part B subgroup for a total of 32 in analysis). Part Z will enroll an additional 21 patients with HER2+ MBC.

PFS-6 will be a binary endpoint with patients surviving progression-free for at least 6 months considered successes; otherwise, patients will be considered failures (including patients who withdraw from the study prior to six months). The ORR and six-month PFS will be presented with two-sided 95% confidence intervals (CIs) (calculated based on the Clopper-Pearson method). The table below shows the precision of the estimates for the two endpoints across a range of sample sizes and ORR or PFS-6 rates.

Projected CIs for ORR and PFS-6

Approximate ORR or PFS-6	N	Percentage (95% CI) [†]	Width of 95% CI [†]
0.20	20	0.20 (0.06, 0.44)	0.38
	25	0.20 (0.07, 0.41)	0.34
	30	0.20 (0.08, 0.39)	0.31
	35	0.20 (0.08, 0.37)	0.28
	40	0.20 (0.09, 0.36)	0.27
0.30	20	0.30 (0.12, 0.54)	0.42
	25	0.32 (0.15, 0.54)	0.39
	30	0.30 (0.15, 0.49)	0.35
	35	0.31 (0.17, 0.49)	0.32
	40	0.30 (0.17, 0.47)	0.30
0.40	20	0.40 (0.19, 0.64)	0.45
	25	0.40 (0.21, 0.61)	0.40
	30	0.40 (0.23, 0.59)	0.37

CONFIDENTIAL

Approximate ORR or PFS-6	N	Percentage (95% CI) [†]	Width of 95% CI [†]
	35	0.40 (0.24, 0.58)	0.34
	40	0.40 (0.25, 0.57)	0.32
0.50	20	0.50 (0.27, 0.73)	0.46
	25	0.52 (0.31, 0.72)	0.41
	30	0.50 (0.31, 0.69)	0.37
	35	0.51 (0.34, 0.69)	0.35
	40	0.50 (0.34, 0.66)	0.32

[†]Based on Clopper-Pearson.

CONFIDENTIAL

BRE 354 SCHEDULE OF ASSESSMENTS (SOA)

Study period	Screening		Treatment Cycles				EOT ^{s,r}	40-Day (+7 days) Safety FU ^t	FU
Cycle ^a			C1	C2	C3	C4+			
Visit number	1		2	3	4	5+			
Treatment day	-28 days ^b	-7 days ^b	1	1 (±2)	1 (±2)	1 (±2)		+1 week	
Informed consent ^b	X								
Inclusion/exclusion criteria	X								
Medical history and demographics ^c		X							
Physical examination, height (screening only), and weight ^{c,d}		X	X	X	X	X	X	X	
ECOG performance status ^{c,d}		X	X	X	X	X	X	X	
12-lead electrocardiograms (triplicate) ^{c,e}	X		X	X	X	X	X		
Ophthalmologic assessments ^f	X						X ^f		
Vital signs ^{c, g}		X	X	X	X	X	X	X	
Serum/urine pregnancy test ^{c,h}		X	X	X	X	X	X	X	
Safety laboratory (hematology, biochemistry) ^{c, i, j}		X	X	X	X	X	X	X	

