Fatigue/ Asthenia/Malaise	Grade 3	Delay dose until resolved to ≤ Grade 1 or baseline, then: 
 • If resolved to ≤ Grade 1 or baseline in ≤14 days, resume patritumab deruxtecan. • If resolved to ≤ Grade 1 or baseline in >14 days, then reduce patritumab deruxtecan by 1 dose level.
Cardiac disorders		

CONFIDENTIAL

	Worst Toxicity NCI CTCAE Version 5.0 Grade (unless otherwise specified)	Schedule Modification for Patritumab deruxtecan
Heart failure	Grade ≥ 2 (Symptoms with moderate activity or exertion)	Cardiologist consultation as necessary. Delay dose until resolved to \leq Grade 1, then reduce patritumab deruxtecan by 1 dose level.
Ejection fraction decreased	Decrease in LVEF 10% - 20% (absolute value), but LVEF $>45\%$	Continue patritumab deruxtecan.
	LVEF 40% - $\leq 45\%$ and decrease is $<10\%$ (absolute value) from baseline	Continue patritumab deruxtecan. Repeat LVEF assessment within 3 weeks.
	LVEF 40% - $\leq 45\%$ and decrease is $\geq 10\%$ to 20% (absolute value) from baseline	Delay patritumab deruxtecan. Repeat LVEF assessment within 3 weeks. If LVEF has not recovered to within 10% (absolute value) from baseline, discontinue patient from study treatment.
	LVEF $<40\%$ or $>20\%$ (absolute value) drop from baseline	Delay patritumab deruxtecan. Repeat LVEF assessment within 3 weeks. If LVEF $<40\%$ or $>20\%$ (absolute value) drop from baseline is confirmed, discontinue patritumab deruxtecan. Cardiologist consultation as necessary.
Electrocardiogram QT corrected interval prolonged	Grade 3 (Average QTcF ≥ 501 ms; >60 ms change from baseline)	Delay patritumab deruxtecan until resolved to \leq Grade 1 (QTcF ≤ 480 ms). Determine if another medication the patient was taking may be responsible and can be adjusted or if there are any changes in serum electrolytes that can be corrected. If QTcF prolongation is attributed to patritumab deruxtecan, then reduce patritumab deruxtecan by 1 dose level. Cardiologist consultation as necessary.
	Grade 4 (Torsade de pointes; polymorphic ventricular tachycardia; signs/symptoms of serious arrhythmia)	Discontinue patient from patritumab deruxtecan. Cardiologist consultation as necessary.

CONFIDENTIAL

	Worst Toxicity NCI CTCAE Version 5.0 Grade (unless otherwise specified)	Schedule Modification for Patritumab deruxtecan
Respiratory, thoracic and mediastinal disorders		

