7.2 Screening

At enrollment, each potential research subject will provide written informed consent ≤ 28 days prior to initiation of treatment and prior to starting any study-specific procedures. Upon signature of the ICF, patients will be assigned a unique patient number as enrollment (screening) occurs.

The screening assessments described in the SOA will be collected, reviewed, and determined to be acceptable by the site Principal Investigator or designee after obtaining informed consent prior to the initiation of treatment.

The following screening assessments should be performed and recorded ≤ 28 days prior to initiation of treatment:

- Ophthalmologic exam
- 12-lead ECG triplicate
- CT scan of chest, abdomen, and pelvis
- Bone scan if bone metastasis is suspected

Ophthalmologic exams include a visual acuity test (early treatment diabetic retinopathy study [ETDRS] or Snellens), slit lamp examination, fundoscopy, and tonometry. Assessments may be

CONFIDENTIAL

repeated as clinically indicated as part of a scheduled or unscheduled visit. A 40 (+7) day FU assessment is required if an on-treatment assessment was abnormal at the time of discontinuation of study therapy, to confirm reversibility of the abnormality.

The following screening assessments should be recorded ≤ 7 days prior to initiation of treatment:

- Medical history and demographics
- Physical examination (including height and weight)
- ECOG performance status
- Vital signs
- Hematology including red blood cell (RBC) count, hemoglobin (Hb), hematocrit, reticulocytes, total white blood cell (WBC) count, absolute neutrophil count (ANC), absolute lymphocyte count, 5-part differential (neutrophils, lymphocytes, monocytes, basophils, eosinophils), and platelet count
- Biochemistry (sodium, potassium, phosphate, chloride, creatinine, calcium, venous bicarbonate HCO_3 or CO_2 , albumin, total protein, AST, ALT, alkaline phosphatase [ALP], bilirubin, lactate dehydrogenase, serum glucose, creatinine kinase [CK: if CK is elevated, then CK-MB, troponin I, and myoglobin should be reactively tested, with further follow-up as clinically warranted], serum urea nitrogen, and serum uric acid)
- Coagulation test - aPTT/PTT and INR/PT
- Urinalysis
- Screening pregnancy test (blood)

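### Table 4 gives heart failure one hold-and-reduce rule for every grade from 2 up, so it permits (but does not require) restart after Grade 4 heart failure, while the other 11 graded Table 4 entries covering Grade 4 stop the drug

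*Combined protocol and SAP*

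**What the plan says.** Table 4 in Section 6.2 has one heart failure row, labelled Grade 2 or higher and described by symptoms on moderate exertion. Its action begins "Cardiologist consultation as necessary. Delay dose until resolved to" Grade 1 or lower, followed by a reduction of one dose level. There is no separate line for Grade 3 or Grade 4.

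In the same cardiac block, the Grade 4 QTc entry reads "Discontinue patient from patritumab deruxtecan. Cardiologist consultation as necessary". The Grade 4 line for other adverse events, at the end of Table 4, reads "Discontinue patient from patritumab deruxtecan". The ejection fraction rows are not graded. The most severe of them requires a repeat measurement and, if LVEF below 40% or a more than 20-point "drop from baseline is confirmed, discontinue patritumab deruxtecan".

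Section 6 sets the general rule. Toxicity of Grade 3 or higher is held until Grade 1 or baseline, and then "Treatment should then be re-instituted, if medically appropriate, at the next lower dose level". Restart also needs confirmed continued benefit by RECIST and a restaging scan in the preceding 6 weeks. A patient with a "toxicity-related dose delay of more than 18 weeks (126 days) from the last patritumab deruxtecan dose must be discontinued", unless extenuating circumstances are discussed with the Medical Monitor.

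For cardiac testing, the Schedule of Assessments lists "12-lead electrocardiograms (triplicate") and has no LVEF row. The Section 7.2 list that opens "The following screening assessments should be performed and recorded" includes the ECG but no LVEF test.

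**The concern.** A Grade 4 event is one that Table 4 itself describes, in several of its rows, as life-threatening and needing urgent intervention. For heart failure at that grade, the printed instruction is the same as for Grade 2: wait for recovery, drop one level and go on. Because heart failure has its own row, the Grade 4 default for other adverse events does not reach it. If the row did not exist, Grade 4 heart failure would be a mandatory stop, so here the specific rule is looser than the default.

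What is at stake is the safety of an individual patient. An investigator following the table could re-expose a patient who has recovered from life-threatening heart failure, with cardiology input only where thought necessary. By contrast, Grade 4 vomiting, diarrhea or mucositis ends treatment outright.

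**Working it through.** No figure in the plan needs reproducing. The check is a count of table entries, followed by a reading of whether other provisions supply the missing stop.

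**Step 1: count Table 4.** The rule is to include every entry whose severity column is a CTCAE grade and covers Grade 4.

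| Entry | Action at Grade 4 |
|---|---|
| Infusion related reaction | Stop (cell read as shared with Grade 3) |
| Heart failure (Grade 2 or higher) | Hold, then reduce one level |
| QTc prolonged | Stop |
| ILD (Grade 3 and 4) | Stop |
| Ocular | Stop |
| Creatinine | Stop |
| AST/ALT without bilirubin rise | Stop |
| Total bilirubin | Stop |
| Vomiting (Grade 4 or higher) | Stop |
| Diarrhea/colitis | Stop |
| Oral mucositis | Stop |
| Other adverse events | Stop |

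Result: 10 stops printed in their own row + 1 stop by a shared cell + 1 hold-and-reduce = 12. Fatigue and nausea are left out because their rows give Grade 3 only. The ejection fraction rows, the combined AST/ALT-and-bilirubin row, the hepatitis row and the general ILD work-up row are left out because they carry no CTCAE grade. The combined liver row can itself end in resumption, but only after drug-induced liver injury is ruled out and the case is discussed with the sponsor.

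**Step 2: count Table 3 in the same way.** Neutrophils, febrile neutropenia, anemia, platelets and lymphocytes make five rows covering Grade 4, and all five allow resumption. Across both tables, 1 + 5 = 6 of 12 + 5 = 17 entries allow restart after Grade 4. The contrast therefore holds within the non-hematologic table only.

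**Step 3: does another provision act as a Grade 4 stop?**

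- Section 6, general rule: restart only if medically appropriate. This is judgement, and its direction is toward restart.
- Section 6, RECIST benefit and the restaging scan: these concern tumor status.
- Section 6, 126 days: a time limit, which the Medical Monitor can discuss extending.
- Section 3.3, intolerable toxicity or intercurrent illness, and Section 7.3.1, unacceptable toxicity: these can end treatment, but by judgement.
- Section 11.2, SAE notice within 24 hours: reporting only.
- LVEF rows of Table 4: a firm stop if LVEF is measured and meets the threshold. No LVEF test is in the Schedule of Assessments or the Section 7.2 list, and the heart failure row does not ask for one.

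None of these is a stop triggered by Grade 4 heart failure itself.

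**Step 4: restart dose.** Under Table 2, a patient at the starting dose would restart at 4.8 mg/kg: (5.6 − 4.8) / 5.6 = 0.143, a reduction of about 14%.

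**The case against.** The strongest reply is that the row breaks no rule. Section 6 makes no exception for Grade 4: it holds any toxicity of Grade 3 or higher and resumes one level lower if appropriate. The heart failure row does the same, and at Grade 2 it is stricter than Section 6, which re-treats without reduction where possible. Nowhere does the protocol say that every Grade 4 non-hematologic event must end treatment, and Table 3 shows that resumption after Grade 4 is acceptable in other settings. All of this stands, and it is why the point is an inconsistency within Table 4 and not a contradiction.

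A second reply is that restart is already well fenced: recovery to Grade 1 or lower, continued tumor benefit, a time limit, and investigator discretion under Section 3.3. This also stands as mitigation. The other 11 Grade 4 stops were nevertheless printed alongside the same safeguards, and the protocol gives no reason for treating heart failure differently from QTc prolongation.

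A third reply is that the event will be rare. Heart failure is neither an identified risk (Section 1.2) nor an event of special interest (Section 11.4). Exclusion criterion 9 in Section 3.2.1 removes patients with LVEF below 50% or with recent NYHA Grade 2 or higher failure. That is accepted.

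Two stronger readings are tempting and should be resisted. A reader might infer that the protocol obliges restart after Grade 4 heart failure. It does not, because Section 6 makes restart conditional on medical judgement. A reader might also try to bound the rate from Section 1.1.3, which lists SAEs seen in more than one of 144 treated patients and does not mention heart failure. That list is by individual term: platelet count decreased (8 patients) and thrombocytopenia (4 patients) appear separately. Several heart failure terms with one patient each could be absent from it and still total more than one. No numerical bound follows.

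**Conclusion.** The point holds as a minor, inexpensive safety improvement. Heart failure is the only one of 12 graded Table 4 entries covering Grade 4 that does not stop the drug, and stopping after such an event depends on general safeguards that are not specific to it. The count rests on two readings: the infusion reaction Grade 4 cell shares the Grade 3 stop, and a specific row displaces the default for other adverse events. The conclusion is confined to the graded entries of Table 4.

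The number of patients affected cannot be estimated, because the documents give no heart failure rate. It is expected to be small among the 121 planned. The definitions of ORR and PFS-6 are not affected.

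**What to change.** At the next amendment, relabel the present heart failure row Grade 2-3 and leave its action unchanged. Below it, add one Grade 4 line with the wording already printed for Grade 4 QTc prolongation: "Discontinue patient from patritumab deruxtecan. Cardiologist consultation as necessary".

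The cost is one changed label and one new line, with no added visits or tests. The downside is that a rare patient who recovers from Grade 4 heart failure could not be re-treated, a consequence the protocol already accepts for the other 11 entries. If the sponsor intends to keep restart available, one sentence giving the reason would serve instead. The absence of a scheduled LVEF test is a separate matter that this change does not address.
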